Nutritional Intervention-Clinical Trial Protocol

Title: Postprandial Inflammatory and Metabolic Responses Induced by the Authentic Ladotyri Mytilinis PDO Cheese and Italian Parmesan PDO Cheese

NCT IDENTIFIER: NCT05788887

16 December 2022

1. Protocol Summary

This is the protocol of a randomized, blinded and controlled nutritional intervention – clinical study to investigate the postprandial effect of consuming Authentic Ladotyri Mytilinis, PDO cheese on the lipid, glycemic profile and the oxidative status of the blood of healthy volunteers.

The acute nutritional intervention – clinical study is a cross over design (acute study), with two axes. The purpose of this study was the investigation of the postprandial metabolic responses, after the intake of a traditional, Ladotyri Mytilinis cheese, compared to corresponding responses after an Italian Parmesan cheese consumption, in healthy participants.

The study volunteers will be healthy, aged 18-65 years, residing during the intervention in Lemnos. The study will take place in the specially designed space of the Human Nutrition Unit, University of the Aegean and in voluntary collaboration with the General Hospital of Limnos. The duration of the study will be 7 days.

Participants will be randomly divided into two groups. During the first day, the first group will consume Italian Parmesan, PDO cheese (control group) and the second group will consume Authentic Ladotyri Mytilinis, PDO cheese (intervention group), together with two slices of bread, while 1 glass of water will be available for each volunteer [1st test period]. After a 7-day washout period, the same volunteers will come to the specially designed area and the process will be repeated, with the difference that the control group of the 1st day will belong to the intervention group, and the intervention group will belong to the control [2nd test period].

In each test period, blood samples will be taken from all consecutive volunteers in a fasted state, as well as 30 minutes, 1.5 and 3 hours after consuming meals. This will be followed by analysis of the samples and statistical processing of the results of the analyzes to present data regarding the acute effect of meal consumption on the postprandial biomarkers of lipemia, glycemia and oxidative stress in healthy volunteers.

2. Theoretical background and study objectives

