2.2. Study Objectives / Research Questions

Purpose

The purpose of this study was the investigation of the postprandial responses on serum total, HDL-, LDL- cholesterol, triglycerides, uric acid, glucose and plasma Total Antioxidant Capacity (TAC), after the intake of a traditional, Authentic Ladotyri Mytilinis cheese, compared to corresponding responses after an Italian Parmesan cheese consumption, in healthy participants.

Research Questions

The research questions of this clinical study are the following:

- ✓ Which is the acute effect of ALM-PDO cheese consumption, in the framework of a high-fat and carbohydrates meal, on the postprandial biomarkers of lipemia, glycemia and oxidative stress?
- ✓ Does the postprandial inflammatory and metabolic responses to ALM-PDO cheese differs, compared to Italian Parmesan PDO cheese? LDL- cholesterol and triglycerides determined at 3h after the meal intake, was set as the primary endpoint of the present, pilot study.

3. Summary presentation / study design

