4.1. Sample size calculation

In order to note a 40% difference in the postprandial response of triglycerides and/or LDL-cholesterol and in order to have an 80% chance of a statistically significant difference between the studied groups at a significance level of 5%, a necessary sample of 10 subjects was calculated.

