6.3. Statistical analysis

After the above analyzes have been carried out using a special biochemical analyzer, the use of the statistical package SPSS (Statistical package for social sciences: SPSS) will follow in order to record, process and analyze the results of the study. The Kolmogorov–Smirnov test was applied to check normality. The main participants' characteristics will be analyzed by descriptive statistics. Differences in baseline values between groups for each biomarker tested, will be analyzed using a paired sample two tailed t test. Repeated ANOVA measures with Geisser–Greenhouse correction will be conducted, for serum total, HDL-, LDL- cholesterol, triglycerides, glucose, uric acid and plasma Total Antioxidant Capacity (TAC). If time or group was significant, multiple comparison post hoc Bonferroni test will be performed for the comparison of concentrations. To check changes in the metabolic biomarkers from baseline to postprandial responses (within-group variation), the Wilcoxon sign-rank test will be carried out.

7. Maintenance of study records

The study files will remain securely registered for a maximum of 3 years from the date of their registration in special areas of the Human Nutrition Unit, University of the Aegean. Study records should be kept for a maximum of 2 years after the last marketing approval, or longer if required by local regulations.

8. Ethics, Consent and Privacy Statement

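### Holm's step-down adjustment would serve the ANOVA follow-up comparisons in section 6.3 at least as well as single-step Bonferroni, with the same 5% family-wise guarantee: a cheap, optional improvement

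*Combined protocol and SAP*

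**What the plan says.** Section 6.3 plans one repeated-measures ANOVA with Geisser-Greenhouse correction for each of seven biomarkers ("for serum total, HDL-, LDL- cholesterol, triglycerides, glucose, uric acid and plasma Total Antioxidant Capacity (TAC"). The follow-up is conditional: "If time or group was significant", then a "multiple comparison post hoc Bonferroni test will be performed for the comparison of concentrations". The section does not list the comparisons or say how many form a family.

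A separate sentence covers change from fasting within a meal: "To check changes in the metabolic biomarkers from baseline to postprandial responses (within-group variation), the Wilcoxon sign-rank test will be carried out". No adjustment is stated for those tests.

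The design sets the possible size of a family. The Protocol Summary gives four sampling times per meal: "blood samples will be taken from all consecutive volunteers in a fasted state, as well as 30 minutes, 1.5 and 3 hours after consuming meals". It also gives two cheeses, crossed over. Section 4.1 states that "a necessary sample of 10 subjects was calculated", for a 40% difference with 80% power at the 5% level. It gives no SD and mentions no post hoc adjustment.

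**The concern.** Single-step Bonferroni tests every comparison in a family of m at 0.05/m, however many of the others have already been rejected. Holm orders the p-values and tests the smallest at 0.05/m, the next at 0.05/(m-1), and so on, stopping at the first failure. Both hold the family-wise error at 5% whatever the correlation between repeated samples, and Holm rejects everything that Bonferroni rejects.

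With 10 volunteers there is little power to spare. Section 2.1 cites earlier work in which a cheese meal raised triglycerides two hours later, so for that marker at least, more than one postprandial sample may truly differ from fasting. That is the setting in which single-step Bonferroni gives up most. At stake is the completeness of the reported postprandial profile: a second or third real difference may be called non-significant when an equally protected procedure would have found it.

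**Working it through.** **Inputs from the documents.** 10 subjects, 80% power, 5% level, 40% difference (section 4.1); four sampling times and two cheeses (Protocol Summary); seven biomarkers, and Bonferroni after a significant time or group effect (section 6.3).

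**Inputs that must be assumed.** Family size m, the SD of the within-subject difference, two-sided testing for the sample size, normal paired differences, and the correlation between comparisons.

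**The plan's own figure.** The 10 subjects cannot be reproduced without an SD, so the effect was solved backwards. For a paired t test with n = 10 and 9 degrees of freedom, power is P(T > t(0.975; 9)), where T is noncentral t with noncentrality d√n. Setting this to 80% gives d = 0.996. The implied SD of the difference is 40%/0.996 = 40.2%. The comparison below therefore uses a true effect of about 1.0 SD.

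**Possible families within one biomarker.**
- Group main effect: two cheeses, so m = 1. Bonferroni and Holm are the same test.
- Cheese against cheese at each sampling time: m = 4, or 3 without the fasting sample.
- All pairs of sampling times: 4 × 3/2 = 6.

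**Thresholds for m = 4, with the power of a single test at each (n = 10, d = 0.996).**
- 0.05/4 = 0.0125: 54.3%
- 0.05/3 = 0.0167: 60.0%
- 0.05/2 = 0.025: 67.8%
- 0.05/1 = 0.05: 80.0%

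Bonferroni stays on the first line throughout. Holm starts there and moves down only after a rejection. The smallest p-value therefore meets the same threshold under both, and the chance of at least one rejection is identical.

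**Simulation, m = 4** (n = 10 paired t tests, at least 40,000 trials per setting, correlation 0 to 0.6). Mean power per real difference:

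| Real differences | Bonferroni | Holm |
|---|---|---|
| 1 of 4 | about 54% | about 54-55% (gain about 0.2 points) |
| 2 of 4 | about 54% | about 58% |
| 3 of 4 | about 54% | 61-62% |

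The chance of detecting all three real differences goes from 16-30% to 30-44%. For scale, Bonferroni with 11 volunteers has 61.4% power per comparison, so the gain with three real differences is worth about one volunteer.

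**Six time pairs.** Under assumed rising profiles the gain per comparison was about 0 to 7 points, for example 47% to 53%.

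**Error control.** Holm rejected everything that Bonferroni rejected in every simulated data set. Family-wise error was at most 5% for both, within simulation error. Where some nulls are true, Holm uses more of the allowance: with m = 4, two real differences and correlation 0.5, it goes from 2.4% to 3.6%.

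**Limit of the check.** The ANOVA gate was not simulated. Both procedures would pass through the same gate, so Holm still cannot reject fewer comparisons, but the absolute power figures are not those of the full planned sequence.

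**The case against.** The strongest reply is that Bonferroni is prespecified, valid and conservative, that no conclusion becomes wrong by using it, and that section 2.2 calls this a pilot study. That stands, and it is why this is a suggestion and not an error.

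Several stronger readings are tempting, and the documents do not support them.

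- *That every secondary comparison is Bonferroni-corrected.* Section 6.3 attaches it only to the ANOVA follow-up. Change from fasting within a meal is also tested by Wilcoxon with no stated adjustment, so such changes would not necessarily go unreported because of Bonferroni.
- *That the main question loses power.* The cheese main effect has one contrast, so the methods coincide. The sample size in 4.1 mentions no post hoc adjustment and is unaffected.
- *That power is given up for nothing.* Bonferroni has simple simultaneous intervals that agree with its tests, and its actual family-wise error is lower when some nulls are true. Section 6.3 plans no intervals, so nothing now specified would be lost, but the trade-off is real.
- *That the size of the gain is known.* It rests on an assumed family and SD, and the larger figures need several differences of about 1.0 SD at once.
- *That Holm would settle multiplicity in this plan.* Used within a biomarker, it leaves the seven biomarkers and the two primary markers ("LDL- cholesterol and triglycerides determined at 3h after the meal intake, was set as the primary endpoint") without a stated adjustment. Those are separate matters.

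A further reply is that Holm cannot be applied until a family is defined. That is true, but the planned Bonferroni needs the same definition, so it does not favour either method.

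**Conclusion.** A cheap improvement. Bonferroni in section 6.3 is valid. Holm keeps the same 5% family-wise guarantee under any dependence and never rejects fewer comparisons, which holds without assumptions about effect size or SD.

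The benefit is conditional. It needs more than one comparison in the family and more than one real difference. With m = 4, 10 pairs and a true effect of about 1.0 SD, it ranges from practically nothing with one real difference to about 7 to 8 percentage points per comparison with three (54% to 61-62%). The trial's actual gain cannot be fixed from the documents.

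**What to change.** In section 6.3, before results are seen, replace the named Bonferroni post hoc test with 'post hoc comparisons with Holm (step-down Bonferroni) adjustment'. Apply it within each biomarker to the same comparisons that would have been Bonferroni-corrected, using the unadjusted p-values from the same model.

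If intervals are reported with the differences, label them as unadjusted or as Bonferroni, because neither will always agree with Holm's decisions: a Bonferroni interval can include zero where Holm rejects, and an unadjusted one can exclude zero where Holm does not.

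The cost is a change of wording and a short hand or spreadsheet step to rank the p-values. No volunteers, samples or new model are needed. The two small downsides are the lack of simple matching simultaneous intervals and an actual family-wise error that sits closer to 5%, but not above it.

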8.1. Ethical standards

The members of the research team agree that they will provide their professional expertise and knowledge to conduct the study in accordance with the requirements of the protocol and in accordance with the provisions of the Declaration of Helsinki and the provisions of the General Data Protection Regulation.

8.2. Rules of ethics and research ethics

During the conduct of this clinical study, all fundamental rules of ethical, scientific and research ethics will be observed. Therefore, an application for the approval of the clinical study will be made by the Bioethics and Research Ethics Committee of the University of the Aegean, with the research volunteers also being informed about its purpose, the confidentiality of the data and the voluntary nature of their participation. Participants will take part in the study after signing a consent form to participate in it.

8.3. Formal consent process

Formal consent in the clinical study is a process that will begin before the enrollment of the interested parties in the study and will continue throughout their participation in it. Those interested will be provided with all the information regarding the benefits and potential risks of the study, as well as a consent form where the necessary procedures will be presented. Every interested party must read it and review it or, in special cases (e.g. blind) be informed by third parties. A copy will be provided to interested parties. The researcher or representative will explain the study and its objectives to each participant and address any questions they may have.

The rights and care of the subjects will be protected by the fact that the quality of their clinical care will not be affected in any way if they refuse to participate in this clinical study. This process will take place at the University where this research will take place.

